3.6.1.6 Disease Control Rate

The stratified Miettinen and Nurminen method will be used for comparison of DCR between the treatment arms. The difference in DCR and its 95% CI from the stratified Miettinen and Nurminen method with strata weighting by sample size will be provided. The same stratification factors used for randomization (protocol Section 6.3.2) will be used as stratification factors in the analysis.

3.6.2 Statistical Methods for Safety Analyses

Safety and tolerability will be assessed by clinical review of all relevant parameters including AEs, laboratory tests, vital signs, and ECG measurements.

The analysis of safety results will follow a tiered approach (Table 4). The tiers differ with respect to the analyses that will be performed. AEs (specific terms as well as system organ class terms) and events that meet predefined limits of change in laboratory, vital signs, and ECG parameters are either prespecified as Tier 1 endpoints or will be classified as belonging to Tier 2 or Tier 3 based on observed proportions of participants with an event.

Tier 1 Events

Safety parameters or AEs of special interest that are identified a priori constitute Tier 1 safety endpoints that will be subject to inferential testing for statistical significance. AEs that are immune-mediated or potentially immune-mediated are well documented and will be evaluated separately; however, these events have been characterized consistently throughout the pembrolizumab clinical development program, and determination of statistical significance is not expected to add value to the safety evaluation. Similarly, the combination

of pembrolizumab and lenvatinib has not been associated with any new safety signals. Therefore, there are no Tier 1 events for this protocol.

Tier 2 Events

Tier 2 parameters will be assessed via point estimates with 95% CIs provided for differences in the proportion of participants with events using the Miettinen and Nurminen method, an unconditional, asymptotic method [Ref. 5.4: 00VMQY].

Membership in Tier 2 requires that at least 10% of participants in any treatment group exhibit the event; all other AEs and predefined limits of change will belong to Tier 3. The threshold of at least 10% of participants was chosen for Tier 2 events because the population enrolled in this study is in critical condition and usually experiences various AEs of similar types regardless of treatment; events reported less frequently than 10% of participants would obscure the assessment of the overall safety profile and add little to the interpretation of potentially meaningful treatment differences. In addition, Grade 3 to 5 AEs ($\geq 5\%$ of participants in 1 of the treatment groups) and SAEs ($\geq 5\%$ of participants in 1 of the treatment groups) will be considered Tier 2 endpoints. Because many 95% CIs may be provided without adjustment for multiplicity, the CIs should be regarded as a helpful descriptive measure to be used in safety review, not as a formal method for assessing the statistical significance of the between-group differences.

Tier 3 Events

Safety endpoints that are not Tier 1 or 2 events are considered Tier 3 events. Only point estimates by treatment group are provided for Tier 3 safety parameters.

Continuous Safety Measures

For continuous measures such as changes from baseline in laboratory, vital signs, and ECG parameters, summary statistics for baseline, on-treatment, and change from baseline values will be provided by treatment group in table format.

To properly account for the potential difference in follow-up time between the study arms, which is expected to be longer in the combo arm, AE incidence adjusted for treatment exposure analyses may be performed as appropriate.

Table 4 Analysis Strategy for Safety Parameters

Safety Tier	Safety Endpoint	95% CI for Treatment Comparison	Descriptive Statistics
Tier 2	Any AE ($\geq 10\%$ of participants in one of the treatment groups)	X	X
	Any Grade 3 to 5 AE ($\geq 5\%$ of participants in one of the treatment groups)	X	X
	Any serious AE ($\geq 5\%$ of participants in one of the treatment groups)	X	X
Tier 3	Any AE		X
	Change from baseline results (laboratory test toxicity grade)		X
Abbreviations: AE = adverse event; CI = confidence interval; X = results will be provided.			

3.6.3 Analysis Methods for Patient-reported Outcome Endpoints

This section describes the planned analyses for the PRO endpoints.

EORTC QLQ-C30 Scoring: Each scale or item is scored between 0 and 100, according to the EORTC QLQ-C30 standard scoring algorithm {04HN7P}. For global health status/quality of life, a higher value indicates a better level of function.

PRO Scoring Algorithm

The QLQ-C30 is composed of both multi-item scales and single-item measures. These include five functional scales, three symptom scales, a global health status / QoL scale, and six single items. Each of the multi-item scales includes a different set of items - no item occurs in more than one scale.

EORTC QLQ-C30 Scoring: All the scales and single-item measures range in score from 0 to 100. A high scale score represents a higher response level.

Thus, a high score for a functional scale represents a *high / healthy level of functioning*, a high score for the global health status / QoL represents a *high QoL*, but a high score for a symptom scale / item represents a *high level of symptomatology / problems.*, according to the EORTC QLQ-C30 standard scoring algorithm [Scott, N. W., et al 2008]. For global health status/QoL and all functional scales, a higher value indicates a better level of function; for symptom scales and single items, a higher value indicates increased severity of symptoms.

According to the QLQ-C30 Manuals, if items I_1, I_2, \dots, I_n are included in a scale, the linear transformation procedure is as follows:

1. Compute the raw score: $RS = (I_1 + I_2 + \dots + I_n) / n$
2. Linear transformation to obtain the score S :

$$\text{Function scales: } S = \left(1 - \frac{RS - 1}{Range}\right) \times 100$$

$$\text{Symptom scales/items: } S = \frac{RS - 1}{Range} \times 100$$

$$\text{Global health status/QoL: } S = \frac{RS - 1}{Range} \times 100$$

Range is the difference between the maximum possible value of RS and the minimum possible value. If more than half of the items within one scale are missing, then the scale is considered missing, otherwise, the score will be calculated as the average score of those available items.

3.6.3.1 PRO Compliance Summary

Completion and compliance of EORTC QLQ-C30/QoL by visit and by treatment will be described. Numbers and percentages of complete and missing data at each visit will be summarized. An instrument is considered complete if at least one valid is available according to the missing item rules outlined in the scoring manual for the instrument.

Completion rate of treated participants (CR-T) at a specific time point is defined as the number of treated participants who complete at least one item over the number of treated participants in the PRO analysis population.

$$CR-T = \frac{\text{Number of treated participants who complete at least one item}}{\text{Number of treated participants in the PRO analysis population}}$$

The completion rate is expected to shrink in the later visit during study period due to the participants who discontinued early. Therefore, another measurement, compliance rate of eligible participants (CR-E) will also be employed as the support for completion rate. CR-E is defined as the number of treated participants who complete at least one item over number of eligible participants who are expected to complete the PRO assessment, not including the participants missing by design such as death, discontinuation, translation not available.

$$CR-E = \frac{\text{Number of treated participants who complete at least one item}}{\text{Number of eligible participants who are expected to complete}}$$

The reasons of non-completion and non-compliance will be provided in supplementary table:

- Completed as scheduled.
- Not completed as scheduled.
- Off-study: not scheduled to be completed.

In addition, reasons for non-completion as scheduled of these measures will be collected using “miss_mode” forms filled by site personnel and will be summarized in table format. The schedule (study visits and estimated study times) and mapping of study visit to analysis visit for PRO data collection is provided in [Table 5](#).

Table 5 PRO Data Collection Schedule* and Mapping of Study visit to Analysis Visit

Data Collection Visit	Scheduled Day	Window of Day Range
Week 1	1	[-28,1]
Week 5	20	[2,43]
Week 8	55	[44,65]
Week 11	77	[66,87]
Week 14	99	[88,109]
Week 17	121	[110,131]
Week 20	143	[132,153]
Week 25	175	[154,219]
Week 36	252	[220,285]
Week 45	318	[286,351]
Week 56	395	[352,439]
Week 69	483	[440,527]
Week 82	571	[528,615]
Week 94	659	[616,703]
Week 105	736	[704,769]
EoT or Safety FU *	796	[770,822]

* If the D/C visit takes place ≥ 30 days from the last dose of study intervention, a safety FU visit is not required. In that event, all procedures required for both the D/C visit and the safety FU visit will be performed at the D/C visit. The D/C date is the date when the participant discontinues all study intervention. SoA as detailed in Protocol 7902-011-00.

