1.3 Schedule of Activities (SoA)

1.3.1 Initial Treatment

As of Amendment 011-04, study participation will end after the final administration of pembrolizumab. Participants who either complete 35 cycles of pembrolizumab or discontinue pembrolizumab will discontinue from the study following the Safety Follow-up visit. AEs and spontaneously reported pregnancies will be reported and followed as described under Section 8. All participants in Efficacy Follow-up prior to initiation of Amendment 011-04 will stop efficacy assessments and be discontinued from the study. All participants in Survival Follow-up prior to the initiation of Amendment 011-04 are considered to have completed the study and should have a final survival contact; these participants will no longer be contacted for survival information. The SoA has been amended to only show the required assessments.

Trial Period	Screening	Treatment Cycle = 21 days						EOT	Posttreatment	Notes	
		1	2	3	4	5	6 to 35		Safety FU ^a		
Visit Timing/ Cycle Number		1	1	1	1	1	1	At D/C	30 days after last dose	All procedures performed before administration of study intervention unless otherwise indicated.	
Cycle Day		1	1	1	1	1	1				
Scheduling Window (days)	-28 to -1	+3	±3	±3	±3	±3	±3		+7		
Informed Consent											
Informed consent	X										
Tumor Tissue Collection											
Archived or newly obtained tumor tissue	X									Archived tissue sample, obtained before screening as part of SOC, may be used.	

Trial Period	Screening	Treatment Cycle = 21 days						EOT	Posttreatment	Notes	
		1	2	3	4	5	6 to 35		Safety FU ^a		
Visit Timing/ Cycle Number								At D/C	30 days after last dose	All procedures performed before administration of study intervention unless otherwise indicated.	
Cycle Day		1	1	1	1	1	1				
Scheduling Window (days)	-28 to -1	+3	±3	±3	±3	±3	±3		+7		
Administrative and General Procedures											
Inclusion/ exclusion criteria	X										
Participant identification card	X	X*								*Update with randomization number from IRT.	
Demographics and medical history	X										
Prior/concomitant medications	X									Per SOC or as clinically indicated and required to be recorded when clinically relevant to an AEOSI, SAE or ECI.	
Treatment randomization		X								First dose within 3 days of randomization.	
Study Intervention Administration											
Pembrolizumab administration IV Q3W		X	X	X	X	X	X				

Trial Period	Screening	Treatment Cycle = 21 days						EOT	Posttreatment	Notes	

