6.6.2 Other Allowed Dose Interruptions for Pembrolizumab

Pembrolizumab may be interrupted for situations other than treatment-related AEs, such as medical/surgical events or logistic reasons not related to study therapy. Participants should be returned to study therapy within 3 weeks of the scheduled interruption, unless otherwise discussed with the Sponsor. The reason for interruption should be documented in the participant's study record. Imaging should not be delayed for delays in treatment cycles.

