8.1.8.1 Timing of Dose Administration

Pembrolizumab: Pembrolizumab will be administered as a 30-minute IV infusion on Day 1 of each 21-day cycle. Sites should make every effort to target the infusion time to be as close to 30 minutes as possible. However, given the variability of infusion pumps from site to site, a window of -5 minutes to +10 minutes is permitted (ie, infusion time is 30 minutes [-5 min/+10 min]).

After Cycle 1 Day 1, pembrolizumab may be administered up to 3 days before or after the scheduled Day 1 of each subsequent cycle due to administrative reasons.

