8.2.2 Patient-reported Outcomes

NOTE: As of Amendment 011-03, PRO questionnaires will no longer be administered to participants.

The EORTC QLQ-C30 and EQ-5D-5L questionnaires will be administered by trained site personnel and completed electronically by participants; EORTC QLQ-C30 should be administered before EQ-5D-5L. The questionnaires should be administered on Day 1 prior to dosing:

- In Cycle 1 to Cycle 7
- In Cycle 9
- In every 3 subsequent cycles through Cycle 18 (Cycles 12, 15, and 18)

- Then in every 4 cycles until the end of study intervention (Cycles 22, 26, 30, and 34)
- At the EOT visit

It is best practice and strongly recommended that electronic patient-reported outcomes (ePROs) be determined for allocated participants before study intervention administration, AE evaluation, and disease status notification. If a participant does not complete the ePRO instruments at a scheduled time point, the MISS_MODE form must be completed to capture the reason that this assessment was not performed.

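### sSAP Table 5 cuts its ePRO windows on a 22-day grid although cycles are 21 days, so on-schedule forms for Cycles 2 to 7 share five rows and Week 20 has no cycle form due

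*SAP*

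**What the plan says.** Protocol 1.3.1 sets "Treatment Cycle = 21 days", and Protocol 8.1.8.1 gives pembrolizumab "on Day 1 of each 21-day cycle", adding that "pembrolizumab may be administered up to 3 days before or after the scheduled Day 1 of each subsequent cycle". Protocol 8.2.2 schedules the questionnaires on Day 1, before dosing, of Cycles 1 to 7, 9, 12, 15, 18, 22, 26, 30 and 34, and also "At the EOT visit". That makes 16 time points.

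sSAP 3.6.3.1, Table 5 ("PRO Data Collection Schedule* and Mapping of Study visit to Analysis Visit") has 16 rows, each with a week label, a scheduled day and a day window. It names no cycles, and its footnote refers to the schedule of the original protocol, which is not among the documents supplied. The section reports completion (CR-T) and compliance (CR-E) by visit. sSAP 3.6.3.2 chooses the time point for the mean-change analysis from those two rates and treats time as categorical in the cLDA model.

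On status, Protocol 9 and 9.4.3 say ePRO endpoints will not be analysed. sSAP 2 and 3.4.3 keep a reduced ePRO output for disclosure, with a 26 July 2021 data cutoff.

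**The concern.** A day-window table should put each on-time form in its own row. A 22-day grid laid over 21-day cycles slips by one day per cycle, so forms completed exactly on time cross into the preceding window. Some rows then hold two scheduled forms and others hold none. A reader of the posted tables would see completion collapse at Week 20 and recover at Week 25, although no cycle questionnaire was due at Week 20. The visit means in the cLDA model would carry wrong or mixed time labels.

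**Working it through.** **Inputs.** Cycle length 21 days and tolerance of 3 days either way (Protocol 1.3.1, 8.1.8.1); questionnaire cycles (Protocol 8.2.2); windows (sSAP Table 5).

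**Table 5's own grid.** The windows from Week 8 on start at days 44, 66, 88, 110, 132, 154, 220, 286, 352, 440, 528, 616, 704 and 770. These are 22 × 2, 3, 4, 5, 6, 7, 10, 13, 16, 20, 24, 28, 32 and 35. With day = 22 × (cycle − 1) + 1, all 15 cycle forms fall one per row; for example, Cycle 7 is day 133, in Week 20. The table therefore works for a 22-day cycle.

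**The protocol's cycle.** With day = 21 × (cycle − 1) + 1, counted from first dose:

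| Cycle | Day | Table 5 row |
|---|---|---|
| 2 | 22 | Week 5 [2,43] |
| 3 | 43 | Week 5 [2,43] |
| 4 | 64 | Week 8 [44,65] |
| 5 | 85 | Week 11 [66,87] |
| 6 | 106 | Week 14 [88,109] |
| 7 | 127 | Week 17 [110,131] |
| none | – | Week 20 [132,153] |
| 9 | 169 | Week 25 [154,219] |
| 12 | 232 | Week 36 [220,285] |
| 15 | 295 | Week 45 [286,351] |
| 18 | 358 | Week 56 [352,439] |
| 22 | 442 | Week 69 [440,527] |
| 26 | 526 | Week 69 [440,527] |
| 30 | 610 | Week 82 [528,615] |
| 34 | 694 | Week 94 [616,703] |
| none | – | Week 105 [704,769] |

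**With the 3-day tolerance.** Cycles 2 to 7 span days 22 − 3 = 19 to 127 + 3 = 130. Days 2 to 131 have five rows, so six forms must share five rows. Cycle 9 cannot come before day 169 − 3 = 166. Likewise Cycles 18 to 34 (five forms, days 355 to 697) lie within days 352 to 703, which have four rows. None of this requires matching rows to cycles.

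**How many forms are misplaced.** This step does need a match. Pairing rows with questionnaire cycles in order is an inference, supported by 16 rows for 16 time points. On it, Cycles 3 to 7 fall short of their row start by 1, 2, 3, 4 and 5 days, and Cycles 26, 30 and 34 by 2, 6 and 10 days: 8 of 14 post-baseline cycle forms. Moving all visits together by −3, −2, −1, 0, +1, +2 or +3 days gives 9, 8, 8, 8, 7, 5 or 4. A shift of +4 gives 3, +5 gives 2, +6 to +9 gives 1, and +10 to +21 gives 0.

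**Who is affected.** Assume discontinuation follows the planning PFS (control median 3.2 months, HR 0.7; sSAP 3.9). The share on treatment at day d is ½[exp(−λd) + exp(−0.7λd)], with λ = ln 2/(3.2 × 30.4375) = 0.00712 per day. This gives 77, 68, 60, 53 and 47% at Cycles 3 to 7, but 4.8, 3.0 and 1.9% at Cycles 26, 30 and 34. The effect sits in the early forms.

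**Week 20 completion (CR-T), simulated.** Assumptions: exponential discontinuation as above, cycle-form completion 90 to 95%, end-of-treatment completion 50 to 90%, all forms mapped by day.
- On schedule (within 3 days): Week 20 is 3 to 5%, against 45 to 49% at Week 17 and about 35 to 39% at Week 25. With a 6.4-month control median it is 2 to 4%, against about 64 to 68% and 56 to 60%.
- With modest assumed dose holds: about 9 to 21% at the 3.2-month median and 11 to 30% at 6.4 months. A second set (holds up to 20 days averaging 0.25 to 1.5 days per cycle, 92% cycle-form and 70% end-of-treatment completion) gave 8 to 23% and 9 to 33%.

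**The case against.** The strongest reply is that real visits run late. Protocol 6.6.2 allows interruptions ("Participants should be returned to study therapy within 3 weeks of the scheduled interruption") and questionnaires follow cycle Day 1, so holds push forms later. On the order match, Table 5 misplaces nothing at common delays of 10 to 21 days. This stands as a limit on size: the near-empty Week 20 row is the on-schedule floor, and actual slippage is not in the documents. It does not rescue the table, which fails when visits are on time or within tolerance.

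The day origin also matters, and Table 5 does not state it. If Day 1 is randomization and first dose follows up to 3 days later, Cycle 7 can reach 127 + 3 + 3 = day 133, inside Week 20, with every tolerance met. The result above is therefore for counting from first dose.

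Stronger readings that a reader might infer, and why they fail:
- *The end-of-treatment row [770,822] cannot be reached.* A completer's on-schedule Cycle 35 is day 21 × 34 + 1 = 715, and the safety visit "30 days after last dose" plus its 7-day window ends at day 752. But Table 5's footnote dates discontinuation from stopping all study intervention, the original design let lenvatinib or placebo continue after pembrolizumab stopped for toxicity (Protocol 1.2), and pembrolizumab interruptions of up to 12 weeks are possible (Protocol 6.6.1). Day 752 is no upper limit. The row is a concern only if end-of-treatment forms are mapped by day, which the sSAP does not say.
- *The Scheduled Day column misplaces forms.* Thirteen of its 14 post-baseline values (Week 5 to Week 105) lie 6 to 42 days from the nearest questionnaire day, but most are window midpoints, and the windows alone place forms.
- *Week 5 completion doubles.* CR-T counts participants, not forms.
- *Nothing at all is due in Week 20.* End-of-treatment forms can fall there; only cycle forms are absent.

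**Conclusion.** The defect is real and minor. Table 5 fits a 22-day cycle and the protocol has a 21-day cycle. Following the table as written, on-schedule forms are pooled in Weeks 5 and 69, and Weeks 20 and 105 have no cycle form due. If the disclosure tables are produced, by-visit CR-T, CR-E and the cLDA means are mislabelled or mixed, chiefly for Cycles 3 to 7. Week 20 completion is artificially low: about 3 to 5% on schedule, roughly 9 to 30% with modest assumed holds.

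The row findings rest on counting from first dose with visits on schedule. The 8-of-14 count rests on the order match, and the percentages rest on the stated discontinuation and completion assumptions. A reader might infer that the comparison between arms is biased or that the mean-change time point moves. Neither is shown: the windows are the same for both arms, and the time point also depends on actual completion, the CR-E denominator and how end-of-treatment forms are mapped. Time to deterioration is largely unaffected, and the output is descriptive.

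**What to change.** First reconcile the protocol (no ePRO analysis) with the sSAP (ePRO kept for disclosure). If the tables are produced, map each form to its analysis visit by nominal cycle and assign end-of-treatment forms by visit type.

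Only if day windows must be used, cut them midway between the 21-day scheduled days: Cycle 2 [2,32], 3 [33,53], 4 [54,74], 5 [75,95], 6 [96,116], 7 [117,148], 9 [149,200], 12 [201,263], 15 [264,326], 18 [327,400], 22 [401,484], 26 [485,568], 30 [569,652], and 34 from day 653 to end of treatment. State the day origin, and where two forms fall in one window use the one closest to the scheduled day. These windows misplace no form for common shifts of −3 to +10 days but misplace Cycles 2 to 6 at delays of 11 to 21 days, which is why nominal-cycle mapping is preferable.

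Then apply the CR-T and CR-E rule to the corrected visits. The cost is one table and a few sentences in the sSAP, plus reprogramming of the visit mapping. No new data are needed.

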8.10.4 Discontinued Participants Continuing to be Monitored in the Study

The discontinuation visit should take place at the time study intervention is discontinued for any reason. If the discontinuation visit takes place 30 days from the last dose of study intervention, at the time of the mandatory safety follow-up visit, the safety visit is not required. All procedures required at the discontinuation visit and at the 30-day safety follow-up visit should be performed.

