3.6.3.2 Mean change from baseline

Change from baseline in the following secondary PRO endpoint from EORTC QLQ C30 will be assessed:

- Global health status/QoL score (EORTC QLQ-C30)

The time point for the mean change from baseline analysis is defined as the latest time point at which CR-T $\geq 60\%$ and CR-E $\geq 80\%$ based on blinded data review prior to the database lock for any PRO analysis and will be documented in a future sSAP amendment.

To assess the treatment effects on the PRO score change from baseline outcomes, a

constrained longitudinal data analysis (cLDA) model proposed by Liang and Zeger [Ref. 5.4: 00QJ0M] will be applied, with the PRO score as the response variable, and treatment, time, the treatment by time interaction, and stratification factors used for randomization (see protocol Section 6.3.2) as covariates.

The treatment difference in terms of least square (LS) mean change from baseline will be estimated from this model together with 95% CI. Model-based LS mean with 95% CI will be provided by treatment group for PROscores at baseline and post-baseline time point.

The cLDA model assumes a common mean across treatment groups at baseline and a different mean for each treatment at each of the post-baseline time points. In this model, the response vector consists of baseline and the values observed at each post-baseline time point. Time is treated as a categorical variable so that no restriction is imposed on the trajectory of the means over time. The cLDA model is specified as follows:

$$E(Y_{ijt}) = \gamma_0 + \gamma_{jt} I(t > 0) + \beta X_{i,j} \quad i=1,2,3,\dots,n; t=0,1,2,3,\dots$$

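### sSAP Table 5 gives the end-of-treatment questionnaire a fixed window of days 770–822, so as written the EoT compliance row is almost empty and end-of-treatment forms fall into cycle rows

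*SAP*

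**What the plan says.** **Collection.** Protocol Section 8.2.2 schedules the questionnaires at Cycles 1 to 7, 9, 12, 15 and 18. It continues: "Then in every 4 cycles until the end of study intervention (Cycles 22, 26, 30, and 34"). One further form is due "At the EOT visit".

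**When that visit happens.** Protocol Section 8.10.4: "The discontinuation visit should take place at the time study intervention is discontinued for any reason". The footnote to sSAP Table 5 agrees: "The D/C date is the date when the participant discontinues all study intervention". Both describe a participant-specific date.

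**Mapping.** sSAP Section 3.6.3.1 says the "mapping of study visit to analysis visit for PRO data collection is provided in" Table 5. Every row of that table has a day range. The row "EoT or Safety FU" has scheduled day 796 and window [770,822]. No text assigns the end-of-treatment form by visit label, and none says what happens when two forms fall in one window.

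**Rates.** CR-T divides completers at a time point by all treated participants in the PRO population, so its denominator is fixed. The CR-E denominator is those expected to complete, "not including the participants missing by design such as death, discontinuation, translation not available".

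**Use of the rates.** sSAP Section 3.6.3.2: "The time point for the mean change from baseline analysis is defined as the latest time point at which CR-T" is at least 60% and CR-E is at least 80%.

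**The concern.** A form whose date is set by the participant's own stopping date cannot be captured by a fixed study-day window. If Table 5 is programmed as printed, a form completed on stopping at day 100 becomes a Week 14 form and one at day 200 a Week 25 form. The EoT row then shows almost no completions, however well the form was collected.

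Two outputs depend on this. The by-visit compliance table is reported, and its EoT row would misdescribe collection. CR-T and CR-E also select the time point of the secondary mean-change analysis. Forms not scheduled for a cycle visit can therefore raise that visit's CR-T and affect which visit is chosen.

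**Working it through.** **1. Can an on-schedule participant reach days 770–822?** Inputs: 21-day cycles (Protocol 8.1.8.1), at most 35 cycles (4.3.3), safety visit 30 days after last dose with a +7 window (SoA 1.3.1). Day 1 of cycle c = 21(c − 1) + 1.

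- Cycle 35 Day 1 = 21 × 34 + 1 = 715.
- Safety visit = 715 + 30 = 745, or 752 with +7.
- Week 105 is [704,769], so both the last dose and the safety visit fall there.
- The printed day 796 is the midpoint of its own window, (770 + 822)/2. The protocol timing does not reproduce it.
- A completer needs accumulated dosing delay of at least 770 − 752 = 18 days for even the latest safety visit to reach the window.
- The ePRO cutoff is 26 July 2021 (sSAP 3.4.3). To reach day 770 by then, a participant had to start by 18 June 2019 (769 days earlier). The documents give no first-randomization date.

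**2. How many stay on treatment that long?** Assumption: time on treatment follows the planned PFS, exponential with median 3.2 months (control) and 3.2/0.7 = 4.57 months (experimental). The share still on treatment at day 715 is 0.6% and 2.9%. So nearly all end-of-treatment forms arise far earlier.

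**3. Which scheduled forms fall in which row?**

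| Row | Window | Scheduled forms (nominal day) |
|---|---|---|
| Week 5 | 2–43 | C2 (22), C3 (43) |
| Week 8 | 44–65 | C4 (64) |
| Week 11 | 66–87 | C5 (85) |
| Week 14 | 88–109 | C6 (106) |
| Week 17 | 110–131 | C7 (127) |
| Week 20 | 132–153 | none |
| Week 25 | 154–219 | C9 (169) |
| Week 94 | 616–703 | C34 (694) |
| Week 105 | 704–769 | none |
| EoT or Safety FU | 770–822 | none |

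Week 20 and Week 105 stay empty of cycle forms even with the ±3-day visit window (C7 at latest day 130, C9 at earliest 166, C34 at latest 697). On schedule they would hold only end-of-treatment forms.

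**4. Effect on CR-T.** The documents give no completion rates. Assume 90% for cycle forms, 80% for end-of-treatment forms, equal arms, and time on treatment as in step 2 (30.44 days per month). Let S(t) be the average share still on treatment t days after day 1. For a row from day L to day H with one cycle form on day c:

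- cycle forms only: CR-T = 0.9 × S(c − 1)
- added by end-of-treatment forms: 0.8 × [S(L − 1) − S(c − 1)] + 0.1 × 0.8 × [S(c − 1) − S(H)]

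Week 11: S(65) = 0.6765, S(84) = 0.6041, S(87) = 0.5934. Cycle forms only: 0.9 × 0.6041 = 54.4%. Added: 0.8 × 0.0724 + 0.08 × 0.0107 = 5.9 points. Total 60.2%. A simulation of the mapping under the same assumptions gave 54.3% and 60.1%. Its results for the early rows:

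| Row | Cycle forms only | With end-of-treatment forms |
|---|---|---|
| Week 5 | 86.3% | 96.2% |
| Week 8 | 61.5% | 68.5% |
| Week 11 | 54.3% | 60.1% |
| Week 14 | 47.9% | 52.9% |
| Week 17 | 42.3% | 46.4% |
| Week 25 | 33.1% | 36.5% |

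The gain over these rows is 3.4 to 9.9 points. In Week 5 it falls to 6.2 points with 50% end-of-treatment completion and to 6.4 with a 6-month median time on treatment.

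**5. Does the 60% criterion move?** In the base case the last row meeting it moves from Week 8 to Week 11, by a margin of 0.1 point. With 50% end-of-treatment completion, Week 11 reaches only 58.1% and nothing moves. With a 6-month median the last row is Week 14 either way (60.5% and 64.4%; Week 17 is 55.8% and 59.1%). A shift is possible but not general.

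**The case against.** **The table may not be meant literally.** Its title speaks of mapping study visits to analysis visits, its introduction calls the times estimated, and its footnote uses a participant-specific discontinuation date. Label mapping may have been intended. That is possible, but no sentence says so, and the only rule printed for the row is days 770–822. If label mapping was intended, one sentence settles it.

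**A reader might infer that CR-E is inflated past the 80% threshold.** That requires counting a stopper's form in the numerator while removing the same person from the denominator. The sSAP does not say this: a participant whose end-of-treatment form was due and completed was expected to complete it and is not missing. Suppose 76% of continuing participants and 85% of stoppers complete a form and 14% stop within the row. Keeping stoppers in both parts gives 0.76 × 0.86 + 0.85 × 0.14 = 77.3%, close to 76% and below 80%. The one-sided ratio can exceed 100%, which would show up on review. CR-T must also reach 60%, so CR-E alone cannot move the time point. The plan's silence on stoppers is a gap, not evidence of inflation.

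**A reader might also want end-of-treatment scores removed from the cLDA visit means.** The documents do not support that as a correction. A score on day 100 is a real observation at day 100, the PRO population follows the ITT principle, and no on-treatment restriction is stated. Dropping the last score before dropout can weaken the missing-at-random assumption in Section 3.6.3.2.

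**The stakes are modest.** This stands. Protocol Section 9.4.3 says ePRO endpoints will not be analyzed, while the sSAP retains items needed for disclosure tables and the registry. Those two statements need reconciling. The time point is also to be fixed by blinded review and a later amendment, so the choice is not automatic.

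**Conclusion.** The point holds for the EoT row and for CR-T. The window of days 770–822 contains no on-schedule end-of-treatment or safety visit, even for a participant completing 35 cycles. As written, the row is almost empty and the forms are spread over the cycle rows, with Week 20 and Week 105 holding only such forms on schedule. This follows from calendar arithmetic and needs no assumption beyond on-schedule dosing.

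The rise in cycle-row CR-T follows if forms are counted by day window, because the denominator is fixed. Its size is illustrative: a few points in most early rows and about 10 in Week 5, under assumed completion rates and planned PFS as a proxy for time on treatment. Whether the selected time point changes cannot be determined from the documents. Nor can the direction or size of any CR-E effect until the treatment of stoppers is stated. The impact is confined to the PRO compliance table and the choice of PRO time point; PFS, OS and ORR are untouched.

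**What to change.** In sSAP Section 3.6.3.1 and Table 5:

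1. Replace the window of days 770–822 with assignment by visit label, or with a window relative to each participant's discontinuation date.
2. State that the day windows apply to scheduled cycle forms when CR-T and CR-E are computed.
3. State that, for any row, a participant is in both the numerator and the denominator of CR-E or in neither.

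End-of-treatment scores can stay in the cLDA model and in time to deterioration at their actual dates. A sentence on which score is used when two fall in one window would complete the rule. Week 20 and Week 105 have no scheduled form, so those rows should be checked against the 21-day grid at the same time.

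The cost is a few lines of sSAP wording and one changed derivation. No new data are needed.
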